8.8.5 Administrative Structure

For this non-interventional study, the Sponsor liaises with a contract research organization for site management and data management. The responsibility of the CRO includes:

- Preparation of all study documents and data repositories (including but not limited to patient information, informed consent, case report form, electronic data base)
- Initiation of participating sites, support of physicians throughout the study and site inspections
- Data analysis
- Reporting of results

No steering committee or expert advisory committee is involved in this study.

8.9 LIMITATIONS OF THE RESEARCH METHOD

As any observational research this study is subject to a series of risks of bias. The potential major ones have been taken into account as much as possible in the design and analysis of the non-interventional study.

The target population of this study is the population of patients treated with cobimetinib / vemurafenib, for metastatic melanoma in a real life setting in Germany. A representative sample of the target population will be drawn, Physicians from hospitals are to identify and recruit the patients. Sample representativeness may be compromised by selection biases.

Additionally the following limitations need to be considered:

- Patient representativeness
- Hospital representativeness
- Information bias
- Measurement errors
- Missing data
- Confounding
- Risk of underrecruiting or overrecruiting

To minimize the risk for the above mentioned biases, certain measurements will be performed. For example this will include, balancing the site selection according to

geography and demographics of melanoma patients in Germany. Minimization of patients lost to follow up will be attempted, by increasing efforts of physicians to contact such patients. Sensitivity analysis will be carried out to investigate bias.

As this is a non-interventional study, mandatory assessments must not be required. Nevertheless data reporting / collection will be conducted in a consistent way, to avoid bias in the data collection process.

This is the first collection of real world data of patients with BRAF mutated locally advanced or metastatic melanoma with or without brain metastases. Due to the unbalance between the two cohorts, and the uncertainty regarding the proportion of both cohorts it was decided to design the study based on two cohorts which will be analyzed separately.

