8.2.2 Study Population

Patients receiving treatment for BRAF V600-mutated unresectable or metastatic mM with a combination of vemurafenib and cobimetinib according to standard of care and in line with the current summary of product characteristics (SmPC)/local labeling and who have no contraindication to a treatment with a combination of vemurafenib and cobimetinib therapy as per the local label are eligible for observation in this non interventional study if the following criteria applies.

Patients must meet the following criteria for study entry:

- Adult patients with unresectable or metastatic melanoma with a BRAF V600 mutation according to SmPC
- Be willing and able to provide informed consent for the non-interventional study.
- Male or female patient being ≥ 18 years of age on day of signing informed consent.
- Histologically confirmed diagnosis of unresectable or metastatic mM (according to the cobimetinib label)
- Presence of BRAF mutation (V600) in tumor tissue prior to enrolment.

Patients who meet any of the following criteria will be excluded from study entry:

- Previous treatment with BRAF- and/or MEK inhibitors prior to study entry
- Hypersensitivity to the active substances or to any of the excipients listed in appendix 4.

Patient selection criteria are as broad as mentioned in the SmPC, with one exception: Patients previously treated with BRAF- and/or MEK inhibitors are excluded. This may lower the number of patients available for recruitment in a further line setting.

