8.3 VARIABLES

8.3.1 Primary Variable

The primary variable for this study is as follows:

- OS: Time interval between start of treatment and date of death for any cause

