9.3 INFORMED CONSENT

The marketing authorization holder's sample Informed Consent Form (and ancillary sample Informed Consent Forms such as a Child's Assent or Caregiver's Informed Consent Form, if applicable) will be provided to each site. If applicable, it will be provided in a certified translation of the local language. The marketing authorization holder must review and approve any proposed deviations from the marketing authorization holder's sample Informed Consent Forms or any alternate Consent Forms proposed by the site (collectively, the "Consent Forms") before IRB/EC submission. The final Consent Forms approved by the IRB/EC must be provided to the marketing authorization holder for health authority submission purposes according to local requirements.

The Consent Forms must be signed and dated by the patient or the patient's legally authorized representative before start of documentation of his or her data in the CRF.

The case history or clinical records for each patient shall document the informed consent process and that written informed consent was obtained prior to first documentation of this patient's data in the CRF.

By signing the form, the patient confirms that he/she has been informed about the study and agrees to pseudonymous data collection, pooling of data with similar scientific data

(if applicable), and the possibility of monitoring activities. It is the responsibility of the physician to obtain written informed consent from each patient participating in the study, after adequate explanation of the aims, methods, anticipated benefits, and potential hazards of the study. The physician must also explain that the patient is completely free to refuse to enter the study or to withdraw from it at any time, for any reason and without losing the benefit of any medical care to which the patient is entitled or is presently receiving.

A copy of each signed Consent Form must be provided to the patient or the patient's legally authorized representative. All signed and dated Consent Forms must remain in each patient's study file or in the site file and must be available for verification by Site Operations Representative at any time.

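### Section 8.9 promises a representative sample, but the protocol sets no rule on which eligible patients a site enrols and mentions no record of those left out, so selection on prognosis could shift median OS outside the confidence interval.

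*Protocol*

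**What the plan says.** Section 8.9 of the protocol defines the target population as patients treated with the combination for metastatic melanoma in real life in Germany. It continues: "A representative sample of the target population will be drawn, Physicians from hospitals are to identify and recruit the patients". The next sentence qualifies this: "Sample representativeness may be compromised by selection biases". Patient representativeness then heads the list of limitations.

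The same section names these measures against bias:
- site balancing by geography and patient demographics ("For example this will include, balancing the site selection according to" introduces it);
- extra effort by physicians to reach patients lost to follow-up;
- consistent data collection;
- a sensitivity analysis: "Sensitivity analysis will be carried out to investigate bias".

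On eligibility, section 8.2.2 says: "Patient selection criteria are as broad as mentioned in the SmPC, with one exception". The exception is earlier treatment with a BRAF or MEK inhibitor. Section 8.3.1 defines the primary variable: "OS: Time interval between start of treatment and date of death for any cause". Under section 9.3, consent must be signed "before start of documentation of his or her data in the CRF". Section 8.5 plans 225 patients at 40 sites, 157 in Cohort A and 68 in Cohort B.

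**The concern.** A sample is representative by design only if a rule decides who enters it, or if those who enter can be compared with those who do not. The protocol states neither. Each site contributes on average 225/40 = 5.6 patients, and the treating physician decides whom to approach.

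There are plausible routes for selection on prognosis. Survival is counted from the start of treatment, but consent is tied only to the start of documentation. A patient who deteriorates or dies soon after starting may never be approached. Entry also requires being able to give consent, which may be harder for patients with symptomatic brain metastases.

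The primary result is a median OS per cohort with no concurrent comparator. For Cohort B, section 8.5 sizes the study so that the lower 95% limit is at least the historical 8 months. A shift caused by who was enrolled feeds straight into that reading, and no later analysis can recover information on patients who were never recorded.

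**Working it through.** **1. Which measures act on patient selection within a site?**
- Site balancing decides which hospitals take part.
- Loss-to-follow-up effort and consistent data collection concern patients already enrolled.
- The sensitivity analysis has no stated input on patients not enrolled. Baseline ECOG, LDH and brain-metastasis details (section 8.4.2, Appendix 2) are recorded for enrolled patients only.
- Sections 8.1, 8.2, 8.4, 8.6, 8.8, 9.3 and Appendix 2 contain no consecutive-enrolment rule, mention no log, and do not tie consent to the start of treatment.

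None of the named measures governs which eligible patients a site enrols.

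**2. The protocol's own precision figures.** Section 8.5 gives, for Cohort B, n = 68 including 10% dropout, median 12 months, 95% CI 8.5 to 15.5. For Cohort A it gives median 25 months, 95% CI 19 to 31. My assumptions are exponential survival, uniform accrual over 18 months, a further 18 months of follow-up, and 10% dropout in both cohorts.

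With L = ln 2 / median, expected events are d = n × [1 − (e^(−18L) − e^(−36L)) / (18L)], and the interval is median ± 1.96 × median / √d.
- Cohort B: n = 68 × 0.9 = 61.2, d = 47.7, interval 8.6 to 15.4.
- Cohort A: n = 157 × 0.9 = 141.3, d = 73.8, interval 19.3 to 30.7.

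Both agree with the protocol to within about 0.3 month. The formula contains sampling error only and has no term for selection.

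**3. Upper-bound illustration of selection.** Suppose the fraction q of eligible patients with the shortest survival is not enrolled. The enrolled median is then the time at which survival in all eligible patients equals 0.5 × (1 − q). Under constant hazard with true median m, this gives t = m × log2[1 / (0.5 × (1 − q))].

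| q | true 8 | true 12 | true 25 |
|---|---|---|---|
| 5% | 8.6 | 12.9 | 26.9 |
| 10% | 9.2 | 13.8 | 28.8 |
| 20% | 10.6 | 15.9 | 33.0 |

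For a true 8 months to appear as 12, 1 + log2[1/(1 − q)] must equal 1.5, so q = 1 − 2^(−0.5) = 29%.

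For scale, the half-width of the stated Cohort B interval is (15.5 − 8.5)/2 = 3.5 months. The shifts from 12 months are 0.9, 1.8 and 3.9 months.

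**4. A milder illustration.** Assume, without support in the documents, that 30% to 50% of treated patients have a poor prognosis with 2 to 3 times the hazard of the others, and that they are enrolled half as often. With poor-prognosis share p and relative enrolment r, the enrolled share is w = pr / (pr + 1 − p). The median solves (1 − w)e^(−λt) + w e^(−hλt) = 0.5, with hazard ratio h and λ set so that r = 1 returns the true median.
- True 8 months: observed 8.8 to 9.8.
- True 12 months: observed 13.1 to 14.7.
- True 25 months: observed 27.4 to 30.5.

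**The case against.** The strongest reply is that section 8.9 exists to declare this limitation, and does so. The sentence after the claim concedes that selection may compromise representativeness. A reader might infer that the protocol hides the risk, and the text does not support that. What stands is narrower: the opening claim is unsupported, and conceding a bias neither limits it nor makes it measurable.

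A reader might also infer that no data on patients left out will be kept. The protocol is only silent. Its list of measures is introduced as examples, and site procedures are partly delegated to stand-alone documents such as the Trial Monitoring Plan, where a log could sit. The supportable statement is that the protocol mentions none.

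Eligibility follows the label with one exception and sets no limit on ECOG or life expectancy, so formal selection on prognosis is small. That is a real merit, but it does not constrain whom a physician approaches among the eligible.

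Baseline prognostic data and the planned Cox regression allow the case mix to be described and results to be examined by prognostic stratum. This partly exposes selection but cannot show how the enrolled differ from all treated patients. Details of the sensitivity analysis may properly be left to a statistical analysis plan. The data it would need must be arranged before enrolment.

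Finally, a per-patient log is not free of constraints. Section 8.6.3 bars creating source data beyond routine, and section 9.3 requires consent before CRF documentation. This objection stands and shapes the fix.

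**Conclusion.** The point holds as an unsupported claim of representativeness without a patient-level safeguard. The median OS in each cohort could be shifted by selection on prognosis, and the confidence interval would not reflect it.

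Size and direction cannot be derived from the documents. The figures of 12.9, 13.8 and 15.9 months from a true 12 are upper bounds: they assume constant hazard and that exactly the shortest survivors are missed. The milder scenario gives 13.1 to 14.7 months and rests on assumed prognostic shares and hazard ratios.

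A reader might infer that omitting 20% would account for the whole planned distance between 8 and 12 months, because the shift from 12 is 3.9 months. That compares a shift starting at 12 with a gap starting at 8. From a true 8 months, 20% gives 10.6, a shift of 2.6 of the 4 months. Nor do the documents establish that the bias would run upwards or be larger in Cohort B; both are only plausible.

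The change is worth making because it is cheap and has to be in place before patients are enrolled.

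**What to change.** 1. In section 8.2.2, require each site to offer participation to every consecutive eligible patient already prescribed the combination while recruitment is open. Treatment choice stays untouched, so the study remains non-interventional.
2. Have sites keep a minimal anonymous tally of eligible patients not enrolled: cohort and reason, plus age group and ECOG where routinely available and permitted. Keep it outside the CRF and word it to be consistent with section 8.6.3 (no source data beyond routine) and section 9.3 (consent before CRF documentation).
3. Report enrolled against tallied patients by cohort, and use the comparison in the sensitivity analysis that section 8.9 already promises.
4. In section 8.9, replace the claim of a representative sample with: *consecutive eligible patients at participating hospitals will be offered participation*. Keep the concession about selection bias. If a log already exists in a stand-alone document, refer to it here.

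The cost is protocol wording and a little site effort for the tally. No visit or test is added.

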8.10 OTHER ASPECTS

n/a

9. PROTECTION OF HUMAN SUBJECTS

9.1 PATIENT DISCONTINUATION

Patients have the right at any time and for any reason to withdraw their consent that their data are collected and used for the study. Reasons for discontinuation of treatment with the medicinal product or withdrawal from the study may include, but are not limited to, the following:

- Patient withdrawal of consent at any time
- Patient is lost to follow-up.

9.1.1 Discontinuation from Treatment with Studied Medicinal Product

The decision for discontinuation from treatment lies with the treating physician in agreement with the patient's decision and is not regulated by this protocol.

The early termination visit should be completed by patients who discontinue treatment with vemurafenib / cobimetinib earlier than planned according to labeling. The primary reason for early treatment discontinuation should be documented on the appropriate CRF page. Every effort should be made to obtain information on patients who discontinue treatment.

9.1.2 Withdrawal from Study

Every effort should be made to obtain information on patients who withdraw from the study. The primary reason for withdrawal from the study should be documented on the appropriate eCRF page. Patients will not be followed for any reason after consent has been withdrawn. Patients who withdraw from the study not be replaced.

9.1.3 Study and Site Discontinuation

The marketing authorization holder has the right to terminate this study at any time. Reasons for terminating the study may include, but are not limited to, the following:

- Patient enrollment is unsatisfactory

The marketing authorization holder will notify the physician if the study is placed on hold, or if the marketing authorization holder decides to discontinue the study.

The marketing authorization holder has the right to replace a site at any time. Reasons for replacing a site may include, but are not limited to, the following:

- Excessively slow recruitment
- Poor protocol adherence
- Inaccurate or incomplete data recording
- Non-compliance with the Guidelines for Good Pharmacoepidemiological Practices (GPP) or any other pertinent local law or guideline

9.2 COMPLIANCE WITH LAWS AND REGULATIONS

This study will be conducted in full conformance with the Guidelines for GPP published by the International Society of Pharmacoepidemiology and the laws and regulations of the country in which the research is conducted.

The study will comply with national and European Union requirements for ensuring the well-being and rights of participants in non-interventional post-authorization safety studies.

9.3 INFORMED CONSENT

The marketing authorization holder's sample Informed Consent Form (and ancillary sample Informed Consent Forms such as a Child's Assent or Caregiver's Informed Consent Form, if applicable) will be provided to each site. If applicable, it will be provided in a certified translation of the local language. The marketing authorization holder must review and approve any proposed deviations from the marketing authorization holder's sample Informed Consent Forms or any alternate Consent Forms proposed by the site (collectively, the "Consent Forms") before IRB/EC submission. The final Consent Forms approved by the IRB/EC must be provided to the marketing authorization holder for health authority submission purposes according to local requirements.

The Consent Forms must be signed and dated by the patient or the patient's legally authorized representative before start of documentation of his or her data in the CRF.

The case history or clinical records for each patient shall document the informed consent process and that written informed consent was obtained prior to first documentation of this patient's data in the CRF.

By signing the form, the patient confirms that he/she has been informed about the study and agrees to pseudonymous data collection, pooling of data with similar scientific data

(if applicable), and the possibility of monitoring activities. It is the responsibility of the physician to obtain written informed consent from each patient participating in the study, after adequate explanation of the aims, methods, anticipated benefits, and potential hazards of the study. The physician must also explain that the patient is completely free to refuse to enter the study or to withdraw from it at any time, for any reason and without losing the benefit of any medical care to which the patient is entitled or is presently receiving.

A copy of each signed Consent Form must be provided to the patient or the patient's legally authorized representative. All signed and dated Consent Forms must remain in each patient's study file or in the site file and must be available for verification by Site Operations Representative at any time.

9.4 INSTITUTIONAL REVIEW BOARD OR ETHICS COMMITTEE

This protocol, the Informed Consent Forms, any information to be given to the patient, and relevant supporting information must be submitted to the IRB/EC by the Site Operations Representative in consultation with the Scientific Responsible and reviewed and approved by the IRB/EC before the study is initiated. In addition, any patient recruitment materials must be approved by the IRB/EC.

In addition to the requirements for collecting and reporting all AEs, adverse events of special interest (AESI), and SAEs to the marketing authorization holder, physicians must comply with requirements for AE reporting to the local health authority and IRB/EC.

9.5 CONFIDENTIALITY

The marketing authorization holder maintains confidentiality standards by coding each patient enrolled in the study through assignment of a unique patient identification number. This means that patient names are not included in datasets that are transmitted to any marketing authorization holder location.

Patient medical information obtained by this study is confidential and may be disclosed to third parties only as permitted by the Informed Consent Form (or separate authorization for use and disclosure of personal health information) signed by the patient, unless permitted or required by law.

Medical information may be given to a patient's personal physician or other appropriate medical personnel responsible for the patient's welfare, for treatment purposes.

Data generated by this study must be available for inspection upon request by representatives of the U.S. FDA and other national and local health authorities, marketing authorization holder monitors, representatives, and collaborators, and the IRB/EC for each study site, as appropriate.

By signing the protocol, the participating physician commits to complying with all related applicable local laws and regulations, as well as any applicable EU regulations, such as the EU Data Privacy Act.

9.6 FINANCIAL DISCLOSURE

Physicians will provide the marketing authorization holder with sufficient, accurate financial information in accordance with local regulations to allow the marketing authorization holder to submit complete and accurate financial certification or disclosure statements to the appropriate health authorities. Physicians are responsible for providing information on financial interests during the course of the study and for 1 year after completion of the study (i.e., LPLV).

10. MANAGEMENT AND REPORTING OF ADVERSE EVENTS/ADVERSE REACTIONS

10.1 SAFETY REPORTING REQUIREMENTS FOR STUDIED MEDICINAL PRODUCTS

10.1.1 Safety Parameters and Definitions

The reporting requirements in this section apply to all studied medicinal products (observational products of interest, as specifically stated in the study Objectives). For safety reporting requirements for non-studied medicinal products, see Section 10.2.

Safety assessments will consist of monitoring and recording SAEs and non-serious AEs (including AEs of special interest), performing safety laboratory assessments, measuring vital signs, and conducting other tests that are deemed critical to the safety evaluation of the study as per standard medical practice.

10.1.1.1 Adverse Events

According to the International Conference of Harmonisation (ICH), an AE is any untoward medical occurrence in a patient or clinical investigation subject administered a pharmaceutical product, regardless of causal attribution. An AE can therefore be any of the following:

- Any unfavorable and unintended sign (including an abnormal laboratory finding), symptom, or disease temporally associated with the use of a medicinal product, whether or not considered related to the medicinal product
- Any new disease or exacerbation of an existing disease (a worsening in the character, frequency, or severity of a known condition), except as described in Appendix 3
- Recurrence of an intermittent medical condition (e.g., headache) not present at baseline
- Any deterioration in a laboratory value or other clinical test (e.g., electrocardiogram [ECG], X-ray) that is associated with symptoms or leads to a change in study treatment or concomitant treatment or discontinuation from study medicine.

10.1.1.2 Assessment of Serious Adverse Events (Immediately Reportable to the Marketing Authorization Holder), Non-serious Adverse Events of Special Interest (AESI) and Other Non-serious Adverse Events

Serious Adverse Events

An SAE is any AE that meets any of the following criteria:

- Is fatal (i.e., the AE actually causes or leads to death)
- Is life-threatening (NOTE: The term “life-threatening” refers to an event in which the patient was at immediate risk of death at the time of the event; it does not refer to an event that hypothetically might have caused death if it were more severe.)
- Requires or prolongs inpatient hospitalization (see A)
- Results in persistent or significant disability/incapacity (i.e., the AE results in substantial disruption of the patient’s ability to conduct normal life functions)
- Is a congenital anomaly/birth defect in a neonate/infant born to a mother exposed to study medicine
- Is a significant medical event in the physician’s judgment (e.g., may jeopardize the patient or may require medical/surgical intervention to prevent one of the outcomes listed above)

The terms “severe” and “serious” are not synonymous. Severity refers to the intensity of an AE (e.g., rated as mild, moderate, or severe, or according to NCI CTCAE criteria; see Appendix 3); the event itself may be of relatively minor medical significance (such as severe headache without any further findings).

Severity and seriousness need to be independently assessed for each AE recorded on the CRF (for detailed instructions, see Appendix 3).

Adverse Events of Special Interest

AEs of special interest for this study include the following:

- Cases of potential medicine-induced liver injury that include an elevated ALT or AST in combination with either an elevated bilirubin or clinical jaundice, as defined by Hy’s law (see Appendix 3).
- Suspected transmission of an infectious agent by the study medicine, as defined below:

Any organism, virus, or infectious particle (e.g., prion protein transmitting transmissible spongiform encephalopathy), pathogenic or non-pathogenic, is considered an infectious agent. A transmission of an infectious agent may be suspected from clinical symptoms or laboratory findings that indicate an infection in a patient exposed to a medicinal product. This term only applies when a contamination of the study medicine is suspected.

- Photosensitivity Grade 3
- Grade \geq 3 rash
- Retinal vein occlusion (RVO), Grade 2
- Visual disturbance, Grade 3
- QTc interval prolongation, Grade 3
- Grade 4 elevations in liver function tests (LFTs)
- Any non-cutaneous primary malignancy will be reported as a **serious** adverse event of special interest
- Any cutaneous primary malignancy, including squamous cell carcinoma (SCC), keratoacanthoma (KA), basal cell carcinoma (BCC), new primary melanoma

The occurrence of any cutaneous primary malignancy, including SCC, KA, BCC, new primary melanoma will be considered a Grade 3 adverse event in this study.

Non-Serious Adverse Events other than Adverse Events of Special Interest

All non-serious AEs (in addition to AEs of special interest) must be collected for this study.

